## **6. COLLECTION OF STUDY VARIABLES**

### **6.1 Recording of data**

The EDC system will be used for data collection and query handling. The investigator will ensure that data are recorded in the eCRFs in accordance with the instructions provided.

The investigator ensures the accuracy, completeness, and timeliness of the data recorded and of the provision of answers to data queries. The investigator will sign the completed eCRFs. A copy of the completed eCRFs will be archived at the study site.

Patient diaries will be used by patients to collect information regarding BMs, degree of straining, stool consistency (BSS), complete/incomplete evacuation, pain level (NRS), use of bisacodyl laxative rescue medication, and use of opioid medication for breakthrough pain.

The patients will be asked to bring the diary to each visit where the diary will be reviewed for accuracy and completeness.

### **6.2 Efficacy**

#### **6.2.1 PAC-SYM**

The PAC-SYM questionnaire [10] is a 12-item questionnaire that evaluates the severity of symptoms of constipation in 3 domains (stool, rectal, and abdominal symptoms) on a 5-point Likert scale ranging from 0 (absent) to 4 (very severe) in the 2 weeks (14 days) prior to assessment. The items of the instrument were developed through literature review and patient interviews. The PAC-SYM has been extensively validated for constipation and is available in several languages that facilitate its use in multinational studies. The questions will take approximately 5 minutes to answer. The PAC-SYM will be administered to patients at Visits 2,3 and 4.

The PAC-SYM questionnaire will be completed by patients on paper forms provided by the study site. Study staff will provide initial instruction on how to fill out the questionnaire. Patients are to fill out the questionnaire in a quiet area, without any help from family, friends, or study staff. Patients are to fill out the PAC-SYM questionnaire prior to any interventions or discussions regarding their OIC with the study staff or the investigator.

#### **6.2.2 PAC-QOL**

The PAC-QOL scale [11] is a 28-item self-report instrument designed to evaluate the burden of constipation on patients' everyday functioning and well-being in the 2 weeks (14 days) prior to assessment. Each item is rated on a 5-point Likert scale ranging from 0 (not at all) to 4 (extremely). The development of the PAC-QOL items was informed by both clinician and patient focus groups and the primary validation study evaluated use of the PAC-QOL in the US, Netherlands, Belgium, Canada, and Australia using French and Dutch translations in addition to the original English language based instrument [11]. The questions will take approximately 5 minutes to answer. The instrument can be used to generate an overall score, but is also reported to assess 4 specific constipation-related domains including: 1) Worries and concerns (11 items), 2) Physical discomfort (4 items), 3) Psychosocial discomfort (8 items), and 4) Satisfaction (5 items).

The PAC-QOL questionnaire will be completed by patients on paper forms provided by the study site. Study staff will provide initial instruction on how to fill out the questionnaire. Patients are to fill out the questionnaire in a quiet area, without any help from family, friends, or study staff. Patients are to fill out the PAC-QOL questionnaire prior to any interventions or discussions regarding their OIC with the study staff or the investigator. The PAC-QOL will be administered to patients at Visits 2, 3 and 4.

### **6.2.3      Diary Measurements**

Paper diaries will be provided to each study subject at the screening visit and study staff will instruct the subject on how to complete the diary. Information to be collected daily will include study drug administration, bowel movements, degree of straining, stool consistency (BSS), complete/incomplete evacuation, pain level (NRS), use of bisacodyl laxative rescue medication, and use of opioid medication for breakthrough pain. At each study visit subject diaries will be collected and a new diary will be dispensed. It is the patient's responsibility to complete the diary, however, under extreme circumstances the caregiver may enter the patient's verbal response to the questions directly into the diary. The study staff will transcribe the subject's responses into the EDC.

### **6.2.4      Bowel movements**

All BMs will be recorded in the diary each day as they occur.

### **6.2.5      Stool consistency (Bristol Stool Scale - BSS)**

Patients will rate stool consistency through completion of the BSS after each BM. The BSS is a medical aid designed to classify the form of human feces into 7 categories. It was developed by Heaton at the University of Bristol and was first published in the Scandinavian Journal of Gastroenterology in 1997 [12]. The form of the stool depends on the time it spends in the colon. The 7 stool types are:

1. Separate hard lumps, like nuts (hard to pass)
2. Sausage-shaped, but lumpy
3. Like sausage, but with cracks on its surface
4. Like a sausage or snake, smooth and soft
5. Soft blobs with clear cut edges (passed easily)
6. Fluffy pieces with ragged edges, a mushy stool
7. Watery, no solid pieces.

Types 1 and 2 indicate constipation, Types 3 and 4 represent "ideal stools," and Types 5 to 7 are tending towards diarrhea or urgency.

### **6.2.6 Degree of Straining**

The degree of straining with each BM will be recorded at the time of the BM and after the BSS. A single-item straining question, developed and validated through 1:1 interviews with OIC patients will be asked and recorded in the diary. The question is provided below:

“How much did you strain during your bowel movement?”

Patients will be asked to respond on a 5 point Likert scale on one of the following options:

1=Not at all

2=A little bit

3=A moderate amount

4=A great deal

5=An extreme amount.

### **6.2.7 Complete/incomplete evacuation**

Patients will record the completeness of evacuation at the time of each BM and after the degree of straining question. A single question on the completeness of evacuation, developed, and validated through 1:1 interviews with OIC patients will be asked and recorded in the diary. The question is provided below:

“Did you feel like your bowels were completely empty after the bowel movement?”

Patients will provide a yes or a no response to the complete/incomplete evacuation question.

### **6.2.8 Pain level**

Patients will rate their pain level at the end of each day, using the NRS for pain (see Section 6.3.6).

### **6.2.9 Use of laxative rescue medication**

All bisacodyl laxative rescue medication will be recorded in the diary on the day it was taken (other laxative rescue medication will be recorded on the concomitant medication eCRF page).

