## 5.5 Concomitant and post-study treatment(s)

It is recognized that some patients may have their pain managed by personal physicians who are not connected with the study. In these cases, the investigator should notify the patient's personal physicians of the patient's participation in the study, and to ask the physician to notify the study investigator should a change in their pain control regimen be made.

Concomitant non-opioid analgesics will not be prohibited, but investigators will be encouraged to maintain such drugs at stable doses on-study if possible.

Contraceptives (eg, oral contraceptive, implant, dermal contraception, long-term injectable contraceptive, intrauterine device) are allowed.

Patients who were on a maintenance bowel regimen (i.e. regular daily schedule) are allowed to continue on that regimen for the duration of the study. Patients who use laxatives on as needed basis (or those who do not use laxatives) will be required to stop all laxatives and other bowel regimens at randomization for the duration of the study. Bisacodyl will be provided at visit 2 for use during the study. During all treatment periods of the study if after a minimum of 48 hours the patient has not experienced a bowel movement they may take bisacodyl rescue therapy (10 to 15 mg dose). However, in the case the patient is unable to wait 48 hours to receive rescue laxative, rescue laxatives may be administered sooner than 48 hours at the discretion of the investigator. If the patient remains constipated, bisacodyl rescue therapy may be repeated up to 2 additional times, as necessary, each 10 to 15 mg doses administered at 12-hour intervals, or the investigator may prescribe a one-time use of an enema. The timing and administration of any rescue therapy used will be noted and recorded in the diary.

Patients will be instructed on the guidelines for rescue bisacodyl use. Patients will be asked to return unused bisacodyl at each subsequent visit. Documentation of bisacodyl use will be reviewed with the patient at each visit by comparing returned bisacodyl with diary records. If there is a discrepancy, the patient will be counseled regarding proper documentation of bisacodyl use in the diary.

Patients will be asked to record their daily opioid breakthrough medication use in the paper diary. Changes in the opioid regimen and laxative regimen may occur at the discretion of the investigator to ensure appropriate symptom management throughout the study.

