##### **10.2.1.1 SBMs Responder Rate**

A SBM is defined as a BM without rescue laxatives in the previous 24 hours. Days with no BMs should be recorded as zero, rather than missing. This diary data will be used to identify SBMs. The weekly SBM frequency within each time period will be calculated for each patient as:

(Total number of SBMs during the time period of interest/number of days) x 7,

where the denominator is the number of days during the time period in which the patient records data. If less than 4 days of data are recorded within a particular week, the data for that week will be considered insufficient and the rate will be set to missing for that week.

A responder is a patient with  $\geq 3$  SBM in a week and at least one SBM/week increase over baseline for the two weeks during which the study drug is taken. For the purposes of the analysis, the proportion of responders will be evaluated during the randomized period, and also during the extension period. The randomized period permits a comparison of response rates for those who received naloxegol and those who received placebo. The responder rate during the extension period for those patients who entered the extension period after having had placebo will be evaluated as supportive of the response rate determined during the randomized period.

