#### **10.2.1.9 Additional Endpoints**

Additional endpoints to be calculated include:

- Doses of rescue laxatives required per week
- Number of enemas required per week
- Number of manual disimpaction procedures required per week

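### The plan conflicts on where non-bisacodyl rescue is recorded and describes no capture of manual disimpaction, so some induced bowel movements could be scored as spontaneous

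*Combined protocol and SAP*

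**What the plan says.** Section 10.2.1.1 gives the analysis rule, "A SBM is defined as a BM without rescue laxatives in the previous 24 hours", and names the data source: "This diary data will be used to identify SBMs".

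Two sets of instructions say where rescue is recorded.

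- Section 5.5 allows bisacodyl rescue. If constipation persists, it allows either repeat doses or the alternative that "the investigator may prescribe a one-time use of an enema". Its next sentence reads "The timing and administration of any rescue therapy used will be noted and recorded in the diary".
- Section 6.2.9 divides the recording. For bisacodyl, "All bisacodyl laxative rescue medication will be recorded in the diary on the day it was taken". For everything else, "other laxative rescue medication will be recorded on the concomitant medication eCRF page". The diary content list in Section 6.2.3 ends with "use of bisacodyl laxative rescue medication, and use of opioid medication for breakthrough pain" and names no other rescue. Section 6.1 gives the same bisacodyl-only item.

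Section 10.2.1.9 lists weekly counts of enemas among the additional endpoints, and also "Number of manual disimpaction procedures required per week". That is the only mention of disimpaction in the document.

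**The concern.** Whether a bowel movement is spontaneous can be decided only if the rescue that preceded it is visible to the derivation, with a time. Three collection sections describe a diary that shows bisacodyl alone, and the derivation is described as working from the diary. On that reading, a movement produced by an enema or another rescue laxative carries no rescue entry and passes as spontaneous.

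Disimpaction is a separate gap. It is not a laxative, so the SBM rule would not exclude a movement recorded after it even if the procedure were perfectly documented, and no documentation of it is described.

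The responder rate, the time to first post-dose SBM, the 24-hour response and the number of days with an SBM all rest on this classification. Efficacy is a secondary aim, but Section 11.1 treats the effect size as critical input to the design of a larger trial.

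**Working it through.** The plan gives no figure to reproduce here. The check compares the sections and then sizes a single error.

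**Where each event is recorded**

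- Bisacodyl: in the diary under Sections 5.5, 6.1, 6.2.3 and 6.2.9. Section 5.5 asks for timing; Section 6.2.9 mentions only the day.
- Enema: in the diary with timing under Section 5.5. Section 6.2.9 does not name enemas, but its residual category of other laxative rescue would send them to the concomitant medication page. Neither diary list includes them.
- Other rescue laxative: the same conflict.
- Manual disimpaction: no diary item, row of the Table 1 schedule or visit task is described.

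**Can the concomitant medication page repair the diary?** Section 10.2.1.1 states no link to it. The Visit 3 and Visit 4 tasks (Sections 3.2.3 and 3.2.4) ask for medications and doses and do not mention clock times. The check of returned drug against diary entries in Section 5.5 covers bisacodyl only. As described, that page would not reliably support a 24-hour window.

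**Effect of one induced movement counted as spontaneous**

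The plan's formula is weekly frequency = (SBMs / days recorded) × 7. One extra movement adds 7 / days recorded:

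- 7 days recorded: 7/7 = 1.0 per week
- 4 days, the minimum for a usable week: 7/4 = 1.75 per week
- 14 days: 7/14 = 0.5 per week

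A responder needs at least 3 SBMs per week and a rise of at least 1 per week over baseline, across the two treatment weeks. The wording leaves open whether the threshold applies week by week or to the two-week average.

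- Single week, 7 days recorded: 2 true plus 1 induced goes from 2.0 to 3.0 and meets the threshold for that week only.
- Two-week average: the threshold is 3 × 2 = 6 SBMs. Five true plus 1 induced goes from 5/2 = 2.5 to 6/2 = 3.0 and crosses. Four true plus 1 induced reaches 5/2 = 2.5 and does not; 4 true plus 2 induced reaches 6/2 = 3.0 and does.

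In every case the rise over baseline must also be met before the patient becomes a responder.

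**Effect on the arm**

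Section 11.1 plans 22 patients per group. Each patient wrongly moved to responder shifts that arm by 1/22 = 4.5 percentage points. The change in the observed difference (naloxegol minus placebo) is (flips on naloxegol − flips on placebo) / 22. For an assumed net imbalance of 1 to 3 patients, this is 1/22 = 4.5 to 3/22 = 13.6 points, toward or away from a treatment effect according to the arm. The range of 1 to 3 is an assumption; the documents give no rate of enema, other rescue or disimpaction use.

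**The case against.** The strongest reply is that Section 5.5 already settles the matter for enemas. Its recording instruction comes directly after the sentence permitting the enema, covers all rescue therapy and asks for timing. Section 6.2.9 never names enemas, and its reference to the day of use may mean only when the entry is made. Section 10.2.1.1 defines an SBM without regard to where the rescue is written down, and does not forbid using concomitant medication data. The enema is also offered to patients who remain constipated after bisacodyl, so some movements after an enema would already fall within 24 hours of a diary-recorded dose.

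Much of this stands. A reader might infer that enemas are definitely kept out of the diary. The documents do not support that: they contradict each other, and the diary form is not among them. Nor do they support saying that bisacodyl is never timed, since Section 5.5 asks for timing, or that the weekly enema count cannot be obtained, since either recording route would supply one. For disimpaction, the accurate statement is that no recording is described; the forms might contain one. Nothing says whether stool removed manually would be entered as a bowel movement. Excluding patients with fecal impaction at entry (Section 4.2) may also make the procedure infrequent.

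The reply does not remove the conflict. The two sections that list the diary's contents and the one that assigns rescue recording all point to bisacodyl only. No sentence tells the programmer to consult another source. The overlap with bisacodyl protects only movements within 24 hours of a dose. The disimpaction endpoint still has no described source.

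**Conclusion.** The concern holds as an unresolved contradiction with a conditional consequence. If the diary follows Sections 6.1, 6.2.3 and 6.2.9, a movement after non-bisacodyl rescue can be scored as spontaneous unless bisacodyl was also taken in the previous 24 hours. If the diary follows Section 5.5, that error does not arise for drug rescue or enemas. The disimpaction gap does not depend on which section is followed: the endpoint has no described collection, and the SBM rule names only laxatives.

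Any single error is modest: 0.5 SBM per week over 14 days and, where it changes a patient's status, 4.5 points on one arm's responder rate. The total cannot be sized.

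A reader might also infer that the errors fall mainly on placebo and so dilute the treatment effect. That would require more rescue or disimpaction on placebo, and the documents give no rates by arm. Similar errors in the baseline week would raise the baseline count and make the required rise harder to meet, which works against response. The direction is therefore unknown. The repair is worth making before data collection, because clock times and undocumented procedures are hard to recover later.

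**What to change.** Bring Sections 6.1, 6.2.3 and 6.2.9 into line with Section 5.5 on recording:

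- Add one diary line, with date and clock time, for any enema, other rescue laxative or manual disimpaction.
- Record the clock time of each bisacodyl dose.
- State in Section 10.2.1.1 that a bowel movement within 24 hours of any of these is not an SBM, and that the derivation uses the diary together with the concomitant medication page.
- Derive the weekly enema and disimpaction counts in Section 10.2.1.9 from the new line.

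No treatment rule changes. The cost is slightly more diary burden for an ill population and slightly fewer movements counted as spontaneous.

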### **6.2.10 Use of opioid medication for breakthrough pain**

Opioid medication for breakthrough pain will be recorded in the diary on the day it was taken.

## 6.3 Safety

The Principal Investigator is responsible for ensuring that all staff involved in the study is familiar with the content of this section.

The federal regulations for the protection of human subjects specify that institutions engaged in research with human subjects must have written procedures for ensuring prompt reporting to the IRB, institutional officials, and any supporting department or agency of any unanticipated problems, including adverse events, involving risks to subjects or others.

According to federal regulations, unanticipated problems are considered reportable to the IRB if they meet ALL of the following criteria:

Involve occurrences that are unexpected (in terms of nature, severity, or frequency) given (a) the research procedures that are described in the protocol-related documents, such as the IRB-approved research protocol and informed consent document, and (b) the characteristics of the subject population being studied [Note: adverse events listed in the investigator's brochure would, by definition, not be considered unexpected]; **AND**

- 1) Related to or possibly related to study activities (in this document, possibly related means there is a reasonable possibility that the incident, experience, or outcome may have been caused by the procedures involved in the research); **AND**
- 2) Are significant enough to suggest that the research may place subjects or others at a greater risk of harm than was previously known or recognized (including physical, psychological, economic, or social harm).

While most unanticipated problems involve adverse physical or psychological events, other types of incidents, experiences or outcomes that occur during the conduct of human subject research may also constitute unanticipated problems as well. For example, in some cases of unanticipated problems no harm occurs, but the event places the study participant into an increased risk of harm (for example if breach of confidentiality occurs).

### 6.3.1 Definition of adverse events

An adverse event is the development of an undesirable medical condition or the deterioration of a pre-existing medical condition following or during exposure to a pharmaceutical product, whether or not considered causally related to the product. An undesirable medical condition can be symptoms (eg, nausea, chest pain), signs (eg, tachycardia, enlarged liver) or the abnormal results of an investigation (eg, laboratory findings, electrocardiogram). In clinical studies, an AE can include an undesirable medical condition occurring at any time, including run-in or washout periods, even if no study treatment has been administered.

The term AE is used to include both serious and non-serious AEs.

Note: Although all AEs must be documented in the study participant's research files (as described below) only some AEs will be determined reportable to the IRB, based on the criteria listed above.

### **6.3.2 Definitions of serious adverse event**

A serious adverse event is an AE occurring during any study phase (ie, screening, double-blind, open label), that fulfils one or more of the following criteria:

- Results in death
- Is immediately life-threatening
- Requires in-patient hospitalization or prolongation of existing hospitalization
- Results in persistent or significant disability/incapacity or substantial disruption of the ability to conduct normal life functions
- Is a congenital abnormality or birth defect
- Is an important medical event that may jeopardize the subject or may require medical intervention to prevent one of the outcomes listed above.

The causality of SAEs (their relationship to all study treatment/procedures) will be assessed by the investigator(s) and communicated to [REDACTED] and [REDACTED].

### **6.3.3 Recording of adverse events**

#### **Time period for collection of adverse events**

All AEs will be collected from the time of signature of informed consent to the follow up visit whether related or not to the IP and must be recorded on the eCRF

#### **Follow-up of unresolved adverse events**

Any AEs that are unresolved at the patient's last AE assessment in the study are followed up by the investigator until resolution or is felt to be stable.

### **Other reporting guidance**

It is important to distinguish between serious and severe AEs. Severity is a measure of intensity whereas seriousness is defined by the criteria above. An AE of severe intensity need not necessarily be considered serious. For example, nausea that persists for several hours may be considered severe nausea, but not a SAE. On the other hand, a stroke that results in only a limited degree of disability may be considered a mild stroke but would be a SAE.

Certain information, although not considered an SAE, must be recorded, reported, and followed up as indicated for an SAE. This includes

- Pregnancy exposure to a study drug. If a pregnancy is confirmed, use of the study drug must be discontinued immediately. Information about pregnancy exposure includes the entire course of pregnancy and delivery, and perinatal and neonatal outcomes, even if there are no abnormal findings. Both maternal and paternal exposures are considered other reportable information. For exposure involving the female partner of a male subject, the necessary

information must be collected from the subject, while respecting the confidentiality of the partner.

- Lactation exposure to a test article with or without an AE
- Overdose of study drug as specified in the protocol with or without an AE.
- Inadvertent or accidental exposure to study drug with or without an AE

In the clinical study report (CSR), the terms used by the investigator to record AEs will be mapped to preferred terms using a standard AE dictionary, Medical Dictionary for Regulatory Activities (MedDRA).

